9.1.7. Confirmatory pregnancy test at the end of follow-up

Urine and/or serum pregnancy test (β -hCG) will be repeated on the final day of follow-up (day 28) for participants who received a pregnancy test at enrolment. The results will be reported in the communication to the DSMB.

9.2. Adverse Event Data Collection

Safety assessments will be performed and recorded by the trial clinicians. All AEs/reactions, observed by the trial clinicians or by the subject, will be accurately documented in the case report form. For each event/reaction the following details will be recorded:

1. Description of the event(s)/reaction(s)
2. Date and time of occurrence
3. Duration
4. Intensity
5. Relationship with the intervention
6. Action taken, including treatment

7. Outcome

In addition, symptoms will be ranked as (1) mild, (2) moderate, or (3) severe, depending on their intensity. All AEs except fever will be judged for their intensity according to the following scale:

- Mild (grade 1): awareness of symptoms that are easily tolerated and do not interfere with usual daily activity
- Moderate (grade 2): discomfort that interferes with or limits usual daily activity
- Severe (grade 3): disabling, with subsequent inability to perform usual daily activity, resulting in absence or required bed rest

For fever, the following scale will be used:

- Mild (grade 1): 37.5 - 38.0°C
- Moderate (grade 2): > 38.0 to 39.0°C
- Severe (grade 3): > 39.0°C

When an AE/SAE occurs, it is the responsibility of the principal investigators and trial clinicians to review all documentation (e.g., hospital progress notes, laboratory, and diagnostics reports) related to the event. The principal investigators and trial clinicians will then record all relevant information regarding an AE/SAE on the Case Report Form (CRF) or SAE Report Form, respectively. Furthermore, the trial clinicians will attempt to establish a diagnosis of the event based on signs, symptoms, and/or other clinical information. In such cases, the diagnosis should be documented as the AE/SAE and not the individual signs/symptoms.

9.3. Haematological severe AE

A haematological severe AE is defined as a drop in Hb density of >40% from baseline. These will be reported separately in the data safety and monitoring reports and in any resulting publications, due to their potential linkage with PQ treatment.

9.4. Assessment of causality

The principal investigators and trial clinicians are obligated to assess the relationship between study procedures and the occurrence of each AE/SAE. The clinicians will use clinical judgment to determine the relationship. Alternative causes, such as natural history of the underlying diseases, concomitant therapy, other risk factors and the temporal relationship of the event to the study procedures will be considered and investigated. The relationship of the AE with the study procedures will be assessed considering the factors listed under the following categories:

Table 7. Causality

Definitely Related	
• reasonable temporal relationship• follows a known response pattern• clear evidence to suggest a causal relationship• there is no alternative aetiology
---------------------------	---

Probably Related	
 • reasonable temporal relationship • follows a suspected response pattern (based on similar agents) • no evidence of a more likely alternative aetiology
Possibly Related	
 • reasonable temporal relationship • little evidence for a more likely alternative aetiology
Unlikely Related	
 • does not have a reasonable temporal relationship 
OR
 
 • good evidence for a more likely alternative aetiology
Not Related	
 • does not have a temporal relationship 
OR
 
 • definitely due to an alternative aetiology

Note: Other factors will also be considered for each causality category when appropriate. Causality assessment is based on available information at the time of the assessment of the AE. The investigator may revise the causality assessment as additional information becomes available.

9.5. Assessment of outcome

Assessment of each AE must be assessed according to the following classification:

Table 8. Outcome

Completely recovered	The subject has fully recovered with no observable residual effects
Not yet completely recovered	The subject condition has improved, but still has some residual effects
Deterioration	The subject's overall condition has worsened
Permanent damage	The AE has resulted in a permanent impairment
Death	The subject died due to the AE
Ongoing	The AE remains the same as at onset
Unknown	The outcome of the AE is not known because of lost to follow-up

All adverse events will be recorded on individual CRF with the following information: the severity grade (mild, moderate, severe), its relationship to the study drug(s) (related/not related), its duration (start and end dates or if continuing at final exam), actions taken, outcome, whether it constitutes a serious adverse event (SAE).

9.6. Data and Safety Monitoring Committee (DSMB)

A Data and Safety Monitoring Committee (DSMB) will be established and convened before the onset of the trial; an independent local safety monitor (LSM) will be appointed in Mali and form part of the DSMB. The DSMB will convene meetings in person or by telephone

conference prior to the study initiation, after the first 50 subjects have been enrolled and upon completion of the study. In addition to these three scheduled meetings, *ad hoc* meetings may be organised based on monthly progress reports that are provided to the DSMB. These monthly reports include an update on the number of participants who were enrolled, who completed the study and who discontinued the study (with reason provided). In addition, key safety data are provided: AEs and up to day 14 haemoglobin concentrations. Any SAEs or Suspected Unexpected Serious Adverse Reactions (SUSARs) are first reported and discussed among the research team and LSM and subsequently reported within 48 hours to the complete DSMB. If an SAE or SUSAR is deemed possibly, probably, or definitely related to the study medication by the DSMB, the trial will be stopped until the DSMB has decided how to proceed or to stop the study.

9.7. Treatment failure criteria

In case a patient develops symptomatic malaria (denoted as fever and the presence of asexual parasitaemia denoted by microscopy) at any time during follow-up, they will be treated with a full course of Dihydroartemisinin-Piperaquine. DP treatment tablets contain 40 mg dihydroartemisinin/320 mg piperaquine (Eurartesim, Sigma Tau) and will be administered per manufacturer guidelines shown in **Table 5**.

Table 9. DP dosing

Body weight (kg)	Daily dose (mg)		Tablet strength and number of tablets
	Piperaquine	DHA	
5 to <7	80	10	½ x 160mg / 20mg tablet
7 to <13	160	20	1 x 160mg / 20mg tablet
13 to <24	320	40	1 x 320mg / 40mg tablet
24 to <36	640	80	2 x 320mg / 40mg tablet
36 to <75	960	120	3 x 320mg / 40mg tablet
75 to 80	1,280	160	4 x 320mg / 40mg tablet
>80	Not eligible		

10. LABORATORY PROCEDURES

10.1. Blood film

Thick and/or thin blood films for parasite counts will be obtained and examined at screening to confirm *P. falciparum* monoinfection. Giemsa-stained thick and/or thin blood films will be examined at a magnification of 100 \times . The blood smear will be considered negative if no parasites are seen after examining 100 high powered fields.

10.2. Gametocyte and asexual stage density measurement

Blood slides stained with Giemsa will be double read over 500 fields for quantification of gametocytes and asexual stages. EDTA samples of blood (200 µL) will be tested for molecular quantification of gametocytes and asexual parasites. Parasite DNA and RNA will be extracted from whole blood samples in EDTA tubes and tested using quantitative real-time polymerase chain reaction (qPCR) with a detection limit of 0.02-0.1 parasites/µL of blood and highly precise parasite quantification [24]. Quantification of gametocytes will be based on sex specific female (Pfs25/CCP4) and male (PfMGET) mRNA detection and quantification by reverse transcriptase-PCR [25]. Markers of asexual stage parasites will include 18s Ribosomal and SBP1 mRNA. Markers of sexual commitment will also be assessed (e.g. Ap2-g).

Further molecular analysis of samples from individuals who have undergone feeding assays (either from whole blood samples or from mosquito midguts) will include parasite genotyping (e.g. to assess clonal complexity or determine the presence of specific deletions e.g. HRP2) and human genotyping for specific genes (HBB, CYP2D6, G6PD).

10.3. Serology and biomarkers

Serological analysis of these samples will include assessment of antibody responses to gametocyte and asexual stage proteins in the microarray platform [26]. Non antibody protein biomarker assessment will be conducted using bead-based assays to assess for correlates of infection and infectivity (i.e. proteins associated with inflammation), or parasite density (HRP2), or parasite proteins linked with gamete activation in the mosquito midgut (i.e Pfg377). If plasma remains after mosquito feeding, some may be stored and used in standard membrane feeding assays in Radboud University, Nijmegen, the Netherlands, for the assessment of functional transmission reducing immunity [27].

10.4. Mosquito infectivity assay

For each assessment of infectivity 2 ml of heparinized blood will be drawn from the study participant and stored at 37°C and transported to the insectary. At the insectary, using standard procedures, ~70 *A. gambiae* will be fed on the subjects' blood for 15-20 minutes (this figure is based on a previous study where 61 fed mosquitoes allowed for an average of 50 mosquitoes surviving until day 7 after the feeding experiment and being available for dissection and examination for oocysts). All of these mosquitoes will be dissected on the 7th day after the feeding assay for prevalence of mosquitoes with oocysts and quantification of oocysts. Infected guts will be stored for later PCR confirmation of oocysts.

10.5. Magnetic-activated cell sorting

Blood samples will be enriched for gametocytes using MACS LS columns as previously described [28].

10.6. Haemoglobin concentrations

Haemoglobin concentrations will be also measured regularly throughout the study using the HemoCue system (Hemocue AB, Angelholm, Sweden).

10.7. Complete blood count

Using standard techniques, the clinical laboratory will perform the complete blood count (CBC) and platelet count. The following CBC parameters will be evaluated for exclusion criteria at baseline and for safety assessment during the study on days 2, 7 and 14: white blood cells, haemoglobin, haematocrit, platelets.

10.8. Biochemistry

Blood chemistries values will be also measured throughout the study. The following parameters will be evaluated for exclusion criteria at baseline and for safety assessment during the study on days 2, 7 and 14: serum creatinine and ALT.

11. DATA MANAGEMENT AND ANALYSIS

All data will be stored on secure password protected databases. Data that are collected on paper forms will be double entered. Data collected through handheld devices or directly produced by laboratory equipment will be examined for quality assurance and fed into the database using double data entry. Handheld devices used for data input and temporary storage will be password protected and data will be encrypted.

11.1. Analysis plan

Mosquito infectivity will be assessed at three levels: the mean number of oocysts in a sample of mosquitoes (i.e. oocyst intensity), the proportion of mosquitoes infected with any number of oocysts (i.e. mosquito infection rate), and the infectivity of the study participant to any number of mosquitoes (i.e. infectivity to mosquitoes). The primary outcome measure will be the percent change in mosquito infection rate within each arm by day 2 compared to baseline, with other time-points of infectivity assessments as secondary outcomes. Percent change will be reported as percent reduction (with 100% as total reduction of transmission, and negative values as enhanced transmission). Other secondary transmission outcomes are as described in the 'Objectives' section above. Some exploratory objectives may be published separately from the main primary/secondary outcomes.

Statistical analysis will be conducted using the most recent STATA and SAS versions (16.0 and SAS version 9.4 at time of writing). Mosquito infection data will be analysed at time-points after baseline only for those individuals who are infectious at baseline, although the data and analyses from all enrolled individuals will be published in the appendix for completeness. Individuals will be classified as infectious to mosquitoes if they infect at least 1 mosquito, with any number of oocysts. Infectivity to mosquitoes and parasite/gametocyte prevalence will be compared within and between treatment arms using generalised linear models (family: binomial, z-score, co-efficient with 95% CI) or fishers exact tests. Absolute haemoglobin density and percent change in haemoglobin density (relative to baseline) will be compared using paired t-tests (t-score for difference compared to day 0) and two-way t-tests (t-score for difference between ACT matched treatment groups at each time-point). The proportion of gametocytes that are male will be calculated for all values with total gametocyte densities of 0.2/ μ L and over. Gametocyte circulation time will be calculated to determine the average period (in days) that a mature gametocyte circulates in the blood prior to clearance, using a deterministic compartmental model that assumes a constant rate of clearance and has a

random effect to account for repeated measures on individuals, as described previously [29]; circulation time will be analysed using t-tests (t score for difference between ACT matched treatment groups) or linear regression analyses. Area under the curve (AUC) of gametocyte density per participant over time will be calculated using the linear trapezoid method [30] using the first 28 days of observation only, and analysed by fitting linear regression models to the log10 adjusted AUC values, with and without adjustment for baseline gametocyte density (t-score, coefficient with 95% CI). All other analyses of quantitative data will be performed using Wilcoxon sign rank tests (z-score for difference compared to matched values at day 0) and Wilcoxon rank-sum tests (z-score for difference between ACT matched treatment arms at each time-point). The nonparametric van Elteren's test, an extension of the Wilcoxon rank sum test, will be used to compare the infectivity between treatment arms after adjusting for gametocyte density, as previously described [19]. This will compare infectivity between groups after stratifying into categories based on total gametocytes per microliter. Within these bins differences in infectivity between arms will be tested, thereby investigating sterilizing effects of gametocytocidal drugs. For all analyses, the threshold for statistical significance will be set at $p < 0.05$.

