3.2. Rationale

Artesunate-Amodiaquine (ASAQ) is a commonly used ACT, however, its transmission reducing efficacy remains largely unknown. Studies microscopically assessing gametocyte carriage post-ASAQ treatment reached very different conclusions, ranging from increased

gametocyte carriage until day 3 [16] or day 7 [17] post-treatment to an immediate decrease in gametocytaemia [18]. Compared to AL, ASAQ appears to be less efficient in preventing post-treatment gametocyte carriage [2]. In addition, it is important to note that gametocyte carriage is a poor measurement for human-to-mosquito transmission, as antimalarial drugs can sterilise gametocytes before removing them from the blood stream [19] and transmissible gametocytes can persist at submicroscopic densities [20]. Membrane feeding assays (MFA) are therefore the most reliable method to assess transmission. MFA can be supported by magnetic enrichment of gametocytes that can allow for assessments of infectivity of increased gametocyte densities [21] and differentiate between lack of infectivity because of gametocyte densities that are too low to permit transmission and gametocyte sterilization [22]. This is relevant since uncertainties remain about the exact working mechanism of transmission-blocking antimalarial drugs that may clear gametocytes, distort their sex-ratio or sterilize gametocytes without clearance from circulation [19]. Understanding the mode by which transmission is prevented can support drug development.

Only one study has performed MFA after ASAQ treatment, reporting an increase in transmission [17]. If there is indeed substantial transmission after treatment with ASAQ, the addition of a single low dose PQ may be considered. To date, the added benefit of PQ when used in combination with ASAQ is unknown.

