5. STUDY DESIGN

This is a five arm, single-blinded, randomized clinical trial. The study will be conducted according to the following steps for each individual:

Individuals aged 10-50 years will be invited to participate. They will be asked to provide informed consent and assent (for those under 18 years of age). After obtaining the informed consent and assent (if applicable), participants will undergo a screening including clinical evaluation and for the presence of microscopically detectable *P. falciparum* infection. Individuals with ≥ 16 gametocytes/ μL will be recruited and go through additional screening including haemoglobin measurement, CBC, assessment of renal and liver functions, and pregnancy tests. Recruitment will continue until 100 infected individuals with microscopically detectable *P. falciparum* gametocytes ($\geq 16/\mu\text{L}$) are recruited and randomised.

Individuals who meet the inclusion and exclusion criteria will be randomised in a 1:1:1:1:1 ratio into five groups (arms); ASAQ, ASAQ-PQ (0.25mg/kg), AL, ALAQ, ALAQ-PQ (**Table 1**). Randomisation will be performed by the study pharmacist. All other staff will be blinded to the treatment allocation.

Table 1. Treatment arms

Arm	ACT	PQ (mg/kg)	Sample size
1	ASAQ		20
2	ASAQ	0.25	20
3	AL		20
4	ALAQ		20
5	ALAQ	0.25	20

Each participant will be followed for 28 days. Participants will receive a full clinical and parasitological examination on days 2, 7, 14, 21, 28 after receiving the first dose of the study drugs. Blood samples will be taken at all visits for parasitology (microscopy, and whole blood for qRT-PCR) and serology with additional samples for haematology and biochemistry analysis at days 0, 2 and 14. A clinical and haematological examination will also be performed on day 1, at which point no other samples will be collected.

Infectivity to locally reared mosquitoes will be assessed with membrane feeding assays at baseline, on the final day of treatment (day 2) and at days 7 and 14 for all participants. Feeds will then be performed at day 21 for any individuals infectious at day 7 or 14; and at day 28 for any individuals infectious at day 14 or 21. Magnetic-activated cell sorting (MACS) to enrich for gametocytes will be done at two timepoints per individual, followed by MFA.

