7. OUTCOME MEASURES

7.1. Primary outcome measure

Median within person percent change (presented as percent reduction) in mosquito infection rate in infectious individuals from baseline (day 0, pre-treatment) to day 2 post treatment in the ASAQ, ASAQ-PQ, AL, ALAQ and ALAQ-PQ arms.

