7.2. Secondary outcome measures

- Median within person percent change (presented as percent reduction) in mosquito infection rate from baseline to all feeding time-points, with comparison within and between arms.
- Median mosquito infection rate at all feeding time-points, with comparison within treatment arms compared to baseline, and between arms.
- Infectivity to mosquitoes at all feeding time-points, with comparison within treatment arms compared to baseline, and between arms.
- Mean oocyst intensity (in all/all infected mosquitoes) at all feeding time-points, with comparison within treatment arms compared to baseline, and between arms.
- Male and female gametocyte prevalence at all time-points, determined by microscopy or molecular assays, with comparison within treatment arms compared to baseline, and between arms.
- Male and female gametocyte density at all time-points, determined by microscopy or molecular assays, with comparison within treatment arms compared to baseline, and between arms.
- Male and female gametocyte sex ratio (proportion male) at all time-points, determined by microscopy or molecular assays, with comparison within treatment arms compared to baseline, and between arms.
- Gametocyte circulation time (cumulative), determined by microscopy or molecular assays, compared between treatment arms.
- Gametocyte area under the curve (cumulative), determined by microscopy or molecular assays, compared between treatment arms.
- Asexual and total parasite prevalence at all time-points, determined by microscopy or molecular assays, with comparison within treatment arms compared to baseline, and between arms.
- Asexual and total parasite density at all time-points, determined by microscopy or molecular assays, with comparison within treatment arms compared to baseline, and between arms.
- Haemoglobin density at all time-points, with comparison within treatment arms compared to baseline, and between arms.
- Median within person percent change (presented as percent reduction) in haemoglobin density from baseline to all time-points, with comparison within and between arms.
- The frequency and prevalence of adverse events (all AE's, treatment related AE's, and haematological AE's) observed up to and including day 2, 7, and 14 post-treatment, and at all timepoints.

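### Section 11.1 limits every post-baseline mosquito outcome to participants infectious on day 0, so the within-arm comparison of yes/no infectivity with baseline starts at 100% and can only stay level or fall

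*Protocol*

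**What the plan says.** Section 11.1 of the protocol describes mosquito infectivity at three levels: oocyst intensity, mosquito infection rate, and whether the participant infects any mosquito at all. A participant counts as infectious if at least one mosquito is infected. The section then sets the analysis set for all three levels: "Mosquito infection data will be analysed at time-points after baseline only for those individuals who are infectious at baseline". The sentence continues: "although the data and analyses from all enrolled individuals will be published in the appendix for completeness".

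The primary outcome in section 7.1 is defined in that same set: "Median within person percent change (presented as percent reduction) in mosquito infection rate in infectious individuals from baseline" to day 2. Section 11.1 reads percent reduction "with 100% as total reduction of transmission, and negative values as enhanced transmission".

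Section 7.2 lists further mosquito outcomes, among them: "Infectivity to mosquitoes at all feeding time-points, with comparison within treatment arms compared to baseline, and between arms". Mosquito infection rate and mean oocyst intensity are listed with the same two comparisons. None of these three needs a non-zero day 0 value to be defined, apart from oocyst intensity when it is taken in infected mosquitoes only.

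Section 5 provides for feeds "at baseline, on the final day of treatment (day 2) and at days 7 and 14 for all participants". The later feeds depend on infectivity after treatment, with no day 0 condition: "Feeds will then be performed at day 21 for any individuals infectious at day 7 or 14", and similarly for day 28.

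**The concern.** The restriction is written for percent change but applied to every mosquito outcome. For yes/no infectivity, the selection rule and the baseline value of the outcome are the same thing. Everyone in the set is infectious on day 0 because that is how they entered it. Later feeds can only keep them infectious or move them to non-infectious. Participants who move the other way are outside the set.

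So a listed secondary comparison, day 0 against each later feed within an arm, is one-directional by construction. A fall there mixes drug effect with the ordinary chance that a weakly infectious person infects one or more of 50 mosquitoes on one day and none on another.

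This matters because section 3.2 cites a single feeding study after ASAQ, which reported more transmission, and links the case for adding PQ to whether transmission after ASAQ is substantial. People who become infectious after treatment are one way in which that could happen, and no listed outcome counts them.

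**Working it through.** **Inputs.** From section 5.4: baseline proportion 17% for the average participant, intra-cluster correlation 0.5, 50 mosquitoes per feed, 20 participants per arm. From section 11.1: infectious means at least 1 infected mosquito. The protocol gives no figure for the share infectious on day 0, so there is none to reproduce. The 88% power in section 5.4 plays no part here.

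**Step 1, no assumptions needed.** Let *d0* and *d2* mark a participant as infectious (1) or not (0) on days 0 and 2. In the restricted set P(*d0* = 1) = 1, so P(*d2* = 1) ≤ P(*d0* = 1) whatever the drug does.

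**Step 2, share left out.** The scale of the correlation is not stated, so I show a range.

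- Logit scale, 17% at the average participant: logit(p) is normal with mean logit(0.17) and variance π²/3, since ICC = σ²/(σ² + π²/3) = 0.5. P(at least 1 of 50 infected) = 1 − E[(1 − p)^50] = 0.91. Left out: 0.09 × 20 ≈ 2 per arm.
- Logit scale, 17% as the population mean: 0.83 infectious. Left out: 0.17 × 20 ≈ 3.5 per arm.
- Beta-binomial, correlation on the probability scale: p ~ Beta(0.17, 0.83), since 1/(0.17 + 0.83 + 1) = 0.5. P(0 of 50) = B(0.17, 50.83)/B(0.17, 0.83) = 0.45. Left out: 0.45 × 20 ≈ 9 per arm.

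The first reading is closest to the mixed effects logistic model that section 5.4 describes.

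**Step 3, what the restricted set shows on day 2.** With no drug effect, the share who lose infectivity equals the share who gain it; call this share *g*. All participants stay level, while the restricted set falls to 1 − *g*/P(*d0* = 1).

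- First logit reading, no visit-to-visit variation: about 0.89 of 20 newly infectious, so *g* = 0.0445 and 1 − 0.0445/0.909 = 0.951.
- Beta-binomial: P(0 of 50 on both days) = B(0.17, 100.83)/B(0.17, 0.83) = 0.403, so *g* = 0.454 − 0.403 = 0.050 and 1 − 0.050/0.546 = 0.908.

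The table also gives simulated results when the odds of mosquito infection truly double. Visit SD is an assumed day-to-day standard deviation on the logit scale, held within the total variance π²/3.

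| Model | True effect | All participants, day 0 → day 2 | Restricted set, day 0 → day 2 | Newly infectious per 20 |
|---|---|---|---|---|
| Logit, visit SD 0 | none | 91% → 91% | 100% → 95% | 0.9 |
| Logit, visit SD 1 | none | 91% → 91% | 100% → 93% | 1.2 |
| Beta-binomial | none | 55% → 55% | 100% → 91% | 1.0 |
| Logit, visit SD 0 | odds doubled | 91% → 95% | 100% → 98% | 1.2 |
| Logit, visit SD 1 | odds doubled | 91% → 95% | 100% → 97% | 1.4 |
| Beta-binomial | odds doubled | 55% → 60% | 100% → 95% | 1.5 |

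When the odds double, infectivity in all participants rises while the restricted set still falls.

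**Step 4, the other mosquito outcomes.** In the restricted set with doubled odds (logit model), the mosquito infection rate rises from 0.289 to 0.393 with visit SD 0, and the median percent reduction is about −27% to −43% across the visit variation tried. A true rise is visible there, with the right sign. With no drug effect, the median reduction created by selection is 0% with no visit variation, about 3% at visit SD 1 and about 17% at visit SD 1.8.

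**The case against.** A reader might infer that the trial cannot see people who become infectious after treatment. The documents do not support that. Everyone is fed on days 0, 2, 7 and 14, the later feeds depend only on infectivity after treatment, and the sentence that sets the restriction goes on to promise analyses, not only data, from all enrolled participants.

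A reader might also infer that the plan reverses the sign of an increase in general. It does not. Section 11.1 provides for negative reductions, and Step 4 shows that both the primary percent change and the restricted infection rate would register a rise. The wrong direction is confined to the yes/no outcome compared with day 0 within an arm.

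Nor are the between-arm comparisons biased. Selection uses a feed taken before treatment, so randomisation holds within the subset. The cost there is fewer participants and a narrower population.

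For the primary outcome the restriction is proper. The artefact it leaves, 17% at most under large assumed visit variation, is small against the 80-90% reduction at issue in section 5.4. Yes/no infectivity is also a weak detector of increases even in all participants: doubling the odds moves it by about one person in 20. The figure of 9 of 20 left out comes from a model that section 5.4 does not describe.

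All of this stands. What it does not answer is Step 1. The main result for a listed secondary outcome is fixed at 100% on day 0, and the analysis that would correct it is placed in an appendix for completeness, with no named role.

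**Conclusion.** The point holds for one outcome and is minor. Under section 11.1 as written, the within-arm comparison of infectivity to mosquitoes with day 0 cannot show an increase. That needs no assumption. The size of the spurious fall with no drug effect, to about 91-95% on day 2, rests on the section 5.4 inputs and on the assumed scale of the correlation. In persons it is about one per arm: 18 × 0.05 ≈ 0.9 under the first logit reading, 11 × 0.09 ≈ 1.0 under the beta-binomial.

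The restriction also leaves about 2 of 20 per arm out of the main analysis of outcomes that are defined for everyone fed (up to 9 of 20 under the beta-binomial reading). Roughly 1 to 1.5 newly infectious participants per arm, expected with no effect or with doubled odds in the table, go uncounted in any listed outcome.

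**What to change.** In section 11.1, confine the baseline-infectious restriction to the percent-change outcomes. For infectivity to mosquitoes, make the analysis of all randomised participants fed on days 0, 2, 7 and 14 the main one, with the restricted set as supportive. For consistency, do the same for mosquito infection rate and for oocyst intensity in all mosquitoes. Report by arm, at each feed, how many participants who were non-infectious on day 0 had become infectious.

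The cost is wording in section 11.1 and a matching line in the statistical analysis plan. No feeds, visits or samples are added, and the all-enrolled analysis is already promised. The one downside is that the estimates will include people with low starting infectivity, which the supportive restricted analysis will show.
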